10.2 Secondary Safety Analysis

The secondary safety variables:

- All cause mortality.
- Rate of symptomatic ICH

The proportion of patients in each group who experience a safety event based on these criteria will be calculated. The CEC/DSMB data supersede the investigator-reported data in all analyses Adverse Events. Rates of symptomatic and asymptomatic hemorrhage will additionally be provided. Frequency counts and percentage of patients within each category will be provided for categorical data. Estimates of the treatment differences and their 95% confidence intervals will be calculated. Subject rates will be compared between treatment groups with Fisher's exact test.

10.3 Analysis of Adverse Events

Tabulations of adverse events will be presented with descriptive statistics at baseline hospitalization and follow-up visits.

Adverse events will be categorized. Adverse event incidence rates will be summarized by category and severity of the adverse event. Each subject will be counted only once within a category by using the adverse event with the highest severity within each category.

All information pertaining to adverse events noted during the study will be listed by subject, detailing verbatim given by the investigator, category, date of onset, date of resolution, causality and severity. The onset of adverse events will also be shown relative (in number of days) to the day of procedure.

A tabulation of Serious Adverse Events (SAEs) will be provided by subject.

The specific categories analyzed will be those that are reported by at least three (3) percent of the patients.

The CEC/DSMB adjudicated data supersedes the investigator reported data in all analyses of adverse events.

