The Penumbra System[®] is a new generation of neuro-embolectomy devices specifically designed to remove thrombus through aspiration.¹⁴⁻¹⁵ The System has received 510(k) clearance from the US FDA for an acute ischemic stroke recanalization indication. The pivotal trial for this clearance was a prospective, single arm, 125 patient study designed to assess the safety and effectiveness of the System to reduce clot burden in acute ischemic stroke, using the Concentric clot retriever (Mountain View, CA) as the predicate device (historical control).¹⁴ The results indicated that the Penumbra System was able to recanalize the site of primary occlusion in over 80% of the patients, which was higher than those reported for the Concentric clot retriever (43% to 54%), or the spontaneous reperfusion rate reported in the untreated control group in the PROACT-II study (18%).^{12,13,19} The high recanalization rate was independent of target vessel locations. Recanalization was successful in 82.6% of patients presenting with occluded target vessels in the ICA, and in 83% of patients presenting with occluded target vessels in the MCA. Among the patients recanalized with the device, 12.8% had procedural complications of which 3.2% were considered serious. None was associated with malfunction or breakage of the device. This procedural event rate is quite favorable when compared to the published rates for other intra-arterial interventions for acute stroke.^{12,13,19,20} These observations are indicative of the ability of the Penumbra System to access the cerebral arteries to safely recanalize the site of primary occlusions in most locations of the brain, and often, in patients with significant tortuosity that would normally hamper intracranial vascular access.

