9.5 Adverse Event Analysis

All adverse events will be summarized by showing the number and percent of patients which report the event. Events will also be reported by relationship to the procedure or device. Causality of adverse events will be adjudicated by a Clinical Events Committee/Data Safety Monitoring Board (CEC/DSMB). Operations of the CEC/DSMB is governed by the CEC/DSMB Charter for this study. The CEC/DSMB data supersede the investigator-reported data in all analyses of adverse events.

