Primary Effectiveness Non-Inferiority: The proportion of patients in the Penumbra System with Separator 3D group who experience TICI 2/3 is no more than .15 below the proportion of patients in the Penumbra System group who experience TICI 2/3.

Additional analyses conducted for secondary endpoints and subgroups will be presented, but not utilized in evaluating the study success or Penumbra System product claims.

3 Sample Size

Approximately 230 patients are to be randomized in a 1:1 ratio to the Penumbra System group (115 patients) or the Penumbra System with Separator 3D group (115 patients).

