3.2 Effectiveness Sample Size Evaluation

The sample size calculations assume that 80% of the standard Penumbra System patients experience success (TICl of 2 to 3) and 80% of the Penumbra System with Separator 3D patients experience success. Based on a binomial non-inferiority analysis with a non-inferiority margin of 15%, a study of 103 patients per group will have 85% power with a one-sided alpha of 0.05. The sample size was adjusted to 115 patients per group to account for up to 10% attrition rate.

Assuming that both the 3D arm and the control arm observe a rate of 80% (82/103), the 95% confidence interval for the difference between groups is (-11.0%, 11.0%). The sample size was calculated for a two-group, one-sided test for two proportions using the normal approximation to the binomial using SAS v 9.2 (SAS Institute, Cary, NC). The output of the proc power procedure for a Pearson Chi-square Test for Two Proportions is provided below.

Computed N Total	
Actual Power	N Total
0.852	206

The sample size calculations support enrolling a total of 230 patients (Table 1).

Table 1. Effectiveness Sample Size Parameters

Penumbra System Success Proportion	0.8
Penumbra System with Separator 3D Success Proportion	0.8
Enrollment Ratio (Control: 3D)	1:1
Power	85%
Alpha	0.05
Number of Sides	1

Null Proportion Difference	-0.15
Sample Size	206 (103 per group)
Estimated Attrition	10%
Total Sample Size	230 (115 per group)

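### SAP 10.3 limits the adverse-event categories analysed to those reported by at least 3% of patients, with no exemption for serious or device-related events, whereas Protocol 9.5 summarises all adverse events

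*SAP*

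**What the plan says.** Protocol 9.5 sets the reporting rule for adverse events: "All adverse events will be summarized by showing the number and percent of patients which report the event". It adds: "Events will also be reported by relationship to the procedure or device". Neither sentence has a frequency threshold.

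SAP 10.3 covers the same ground and ends with a restriction: "The specific categories analyzed will be those that are reported by at least three (3) percent of the patients". It does not say whether the percentage is of all patients or of one arm, or whether being analysed means being summarised, tested or displayed separately. It makes no exception for SAEs or for events related to the device or procedure. Causality appears in SAP 10.3 only as a field in the by-subject listing, and no summary by relationship is described.

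The same section also promises, without a cut-off, incidence rates by category and severity, a by-subject listing of all events, and a by-subject tabulation of SAEs. Elsewhere, with no frequency threshold:

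- SAP 10.1 compares device- or procedure-related SAEs within 24 hours between arms.
- SAP 10.2 and 10.5 compare mortality and symptomatic ICH, and SAP 10.2 also gives asymptomatic hemorrhage rates.

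SAP 10.4 applies Bonferroni to all safety comparisons without stating how many there are.

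**The concern.** SAP section 1 describes the SAP as elaborating the methods outlined in the protocol. Here it appears to narrow them without saying so.

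The cut-off also falls where the events of interest in a device trial are likely to lie. The Protocol Introduction reports for the sponsor's 125-patient pivotal study that "12.8% had procedural complications of which 3.2% were considered serious". If all serious procedural complications together amount to about 3%, a single type such as perforation or dissection would usually fall below a 3% threshold.

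At stake is whether the report shows how often each uncommon event occurred in each arm. A by-subject listing lets a reader count the cases, but it is not a rate by arm and is not the number and percent that the protocol promises.

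**Working it through.** **1. The denominator.** SAP section 3: "Approximately 230 patients are to be randomized in a 1:1 ratio", that is 115 per arm. The basis is in SAP 3.2: 80% success in each arm, and a "non-inferiority margin of 15%, a study of 103 patients per group will have 85% power with a one-sided alpha of 0.05".

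- n per group = (1.645 + 1.036)² × (0.8 × 0.2 + 0.8 × 0.2) / 0.15² = 7.19 × 0.32 / 0.0225 = 102.2, so 103.
- Power at 103 = Φ(0.15 / √(0.32/103) − 1.645) = Φ(1.046) = 0.852, as the SAP prints.
- Attrition: 103 / 0.90 = 114.4, so 115 per group and 230 in total.

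The plan's figures reproduce.

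**2. The threshold, pooled reading.** 0.03 × 230 = 6.9, so a category needs 7 patients. Six patients are 6/230 = 2.6% and are left out. With 206 patients, 0.03 × 206 = 6.18, so the threshold is again 7 (6/206 = 2.9%).

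**3. Where serious procedural events would fall.** 12.8% and 3.2% of 125 are 16 and 4 patients, so the 3.2% reads as a share of patients and not of the complications. Carried over to this trial (an assumption), 0.032 × 230 = 7.4 patients for all serious types combined. One type alone would usually have fewer than 7.

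**4. How large an excess can be left out.** For a v 0 with equal arms of 115, the two-sided Fisher p is 2 × C(115, a) / C(230, a).

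| Split | Pooled % | Fisher p | Pooled 3% rule | Per-arm 3% rule |
|---|---|---|---|---|
| 3 v 0 | 1.3 | 0.247 | left out | left out |
| 4 v 0 | 1.7 | 0.122 | left out | analysed |
| 5 v 0 | 2.2 | 0.060 | left out | analysed |
| 5 v 1 | 2.6 | 0.213 | left out | analysed |
| 6 v 0 | 2.6 | 0.029 | left out | analysed |

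On the per-arm reading 0.03 × 115 = 3.45, so 4 patients in one arm suffice. At 103 per arm the pooled pattern is the same (6 v 0: 0.029; 5 v 0: 0.059).

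**5. Against the SAP's own multiplicity rule.** Bonferroni with two comparisons gives 0.05 / 2 = 0.025. Since 0.029 > 0.025, 6 v 0 fails for any number of comparisons from two upwards.

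**6. Unequal arms.** Safety is analysed by treatment received (SAP 5.1), so arms may differ in size. At an assumed 110 v 120 with all events in the smaller arm, 5 v 0 gives 0.024 and 6 v 0 gives 0.011. Both are still left out on the pooled reading.

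**7. How often this could occur.** Assume, for illustration, a true rate r in the 3D arm and none in control. The chance that a category is seen but has only 1 to 6 patients of 115 is 91% at r = 3%, 81% at 4%, 64% at 5% and 46% at 6%.

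**The case against.** The strongest reply is that little of clinical weight is lost. A serious related perforation or dissection within 24 hours counts in the primary safety endpoint whatever its frequency. Protocol 9.4.1 adds counts, percentages and differences with 95% confidence intervals for that endpoint. Death and hemorrhage are reported by group. All events are listed with causality. SAP 10.3 itself promises incidence by category and severity, so if being analysed there means being tested, every category is still summarised. Study success rests on TICI alone (SAP section 2).

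Much of this stands, and it limits the point. It does not remove it. The 24-hour endpoint is a composite, in which an excess of one event type can be offset by others, and it excludes later related SAEs and non-serious device events. The listing and the SAE tabulation are by subject. The cut-off sentence comes last in its section on what is analysed and can be read as governing the incidence summary. Even on the favourable reading, the SAP has no summary by relationship.

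A reader might infer two stronger things:

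- **That the rule would hide a significant excess of a device event.** The documents do not support this as a general statement. At equal arms only 6 v 0 is both left out and below 0.05. It fails the SAP's own Bonferroni rule with two or more comparisons, and it would be analysed on a per-arm reading.
- **That the SAP drops a between-arm test or confidence interval required by Protocol 9.5.** It does not. Protocol 9.5 promises number and percent and reporting by relationship, with no test or interval for each category.

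**Conclusion.** The conflict between SAP 10.3 and Protocol 9.5 is real and does not depend on any p-value. One document summarises all adverse events, and by relationship. The other limits the categories analysed to 3% or more, without defining the denominator and without exempting serious or related events.

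The practical gap is narrower than the rule first suggests. It concerns individual categories below 3% (6 or fewer of 230 patients on the pooled reading), chiefly non-serious device events and related SAEs after 24 hours other than death and hemorrhage. These may have no rate by arm. The 6 v 0 example, 5.2% v 0%, shows the largest one-sided split that can go unreported at equal arms. It is a nominal result and not a finding under the SAP's rules.

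This rests on reading the 3% as pooled and on arms of 115 or 103. On a per-arm reading, the largest one-sided excess left out is 3 v 0 (p = 0.247). The trial's success criterion is unaffected, but the wording should be corrected before database lock.

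**What to change.** In SAP 10.3:

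- Summarise every adverse-event category by arm and by relationship to device and procedure, with counts and percentages, in line with Protocol 9.5.
- State the denominator of the 3% rule (pooled or per arm, and which population), and use the rule only to select a display of common events.
- Exempt SAEs and device- or procedure-related events from the rule.
- Say what being analysed means in that sentence.

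A difference with a 95% confidence interval for serious and related categories would be a useful descriptive addition, but it is optional, because Protocol 9.5 does not call for it. The cost is longer tables, with no new data and no effect on sample size or on the primary analysis.

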10.4 Handling of Multiplicity

All safety variable comparisons between the Penumbra System versus the Penumbra System with Separator 3D will be considered secondary analyses and will be adjusted using the Bonferroni correction.

10.5 Analysis of Deaths

The Kaplan-Meier product-limit method will be the primary method utilized to assess the mortality rate. With the date of procedure set at Day 0, any death occurring on or before calendar day 90 will be counted as a death. If clinical assessment is missing for a patient who has not died, the patient will be censored at the last follow-up date. Patients who are alive at day 90 will be censored at day 90. The log-rank test will be used to compare the groups. This comparison weights earlier and later differences equally. The time to death will be plotted with confidence intervals at monthly intervals.

Additionally, the death data will be presented as 90 Day binary deaths. The number of deaths will be presented for each group.

11 Pooling Across Centers

The clinical study will be conducted under a common protocol for each investigational center with the intention of pooling the data for analysis. Every effort will be made to promote

consistency in study execution at each investigational center. Analyses will be presented using data pooled across centers. Appropriate stratification and multivariate techniques, including contingency tables and logistic regression for binary outcomes, analysis of variance for continuous measures, and proportional hazards regression for time-to-event outcomes, will be used to assess differences between study centers to justify pooling data across centers. Centers with fewer than 10 patients will be combined and treated as one site in the pooling analysis.

12 Lost to Follow-Up and Missing Data

For sensitivity purposes, the following additional analyses will be conducted:

- Analyze only patients with complete primary endpoint data.
- For those patients without any observations after randomization, their final observations will be imputed by baseline scores and included in an analysis.
- A tipping point analysis will be conducted in which the missing data will be replaced with values such that the p-value is equal to the significance level.

13 Committees

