9.4 Safety

The denominator for the safety analyses is all enrolled patients who received the assigned treatment in the target vessel.

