9.4.2 Secondary Safety Analysis

- Analysis of symptomatic ICH: Rates of symptomatic and asymptomatic hemorrhage will additionally be provided. Frequency counts and percentage of subjects within each category will be provided for categorical data. Estimates of the treatment differences and their 95% confidence intervals will be calculated. Patient rates will be compared between treatment groups with Fisher's exact test.
- Analysis of Deaths: The Kaplan-Meier product-limit method will be the primary method utilized to assess the mortality rate. With the date of randomization set at Day 0, any death occurring on or before calendar day 90 will be counted as a death. If clinical assessment is missing for a patient who has not died, the patient will be censored at the last follow-up date. Patients who are alive at day 90 will be censored at day 90. The log-rank test will be used to compare the groups. This comparison weights earlier and later differences equally. Additionally, the death data will be presented as 90 Day binary deaths. The number of deaths will be presented for each group.

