5.1 Definitions

All primary and secondary effectiveness endpoints will be performed for both the intent-to-treat (ITT) population and per-protocol (PP) population.

The ITT population will consist of all patients who signed the informed consent and are randomized in the study. The data from the ITT population will be analyzed by the treatment group assignment given at the time of randomization, even if the subject does not receive the correct treatment, or does not follow the protocol until completion. All randomized patients will

be followed and assessed for 90 days post-procedure, even when no neurothrombectomy is performed.

For the PP analysis, only patients who actually received the assigned treatment and do not have major protocol violations will be included.

For the safety analysis, patients will be analyzed according to the treatment they received.

Any treated patients who are not randomized through the IVRS system will be excluded from all analyses. The reason(s) for their exclusion from the study will be recorded. Listings will be provided for these patients, and they will be discussed in the clinical report.

Roll-in patients will be followed for 90 days and their safety will be summarized separately in the clinical report.

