10.1 Primary Safety Analysis

The primary safety endpoint is the proportion of patients with a device or procedure related SAE within 24 hours post-procedure. The proportion of patients in each group who meet the safety endpoint based on this criterion will be calculated.

The primary null hypothesis for safety in this study is that there is no difference in device-related and procedure-related serious adverse event rates. This null hypothesis will be tested against the alternative hypothesis that there is a difference between the two treatment groups. The null hypothesis will be rejected at the two-sided significance level of $\alpha = 0.05$. The primary analysis is an analysis of all patients according to treatment received. The Fisher's Exact test will be employed to assess the primary safety endpoint.

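### All-cause mortality has conflicting time origins and populations in the protocol and SAP, and no overall comparison by randomised arm is planned

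*SAP*

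**What the plan says.** All-cause mortality is a secondary endpoint (Protocol 2.2.2) and a secondary safety variable (SAP 10.2). It is to be analysed by Kaplan-Meier with a log-rank test, and also as 90-day binary deaths.

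**Time origin.** Protocol 9.4.2: "With the date of randomization set at Day 0, any death occurring on or before calendar day 90 will be counted as a death". SAP 10.5 gives the same 90-day rule but opens it differently: "With the date of procedure set at Day 0".

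**Population.** Protocol 9.4, which governs 9.4.2, states: "The denominator for the safety analyses is all enrolled patients who received the assigned treatment in the target vessel". SAP 5.1 states: "For the safety analysis, patients will be analyzed according to the treatment they received". SAP 10.1 says the same for the 24-hour serious adverse event endpoint: "The primary analysis is an analysis of all patients according to treatment received". SAP 10.5 names no population. SAP 8 will count a safety population, but SAP 5.1 does not say who belongs to it. SAP 5.1 assigns the overall ITT and per-protocol analyses to the effectiveness endpoints only. SAP 9.4 nevertheless runs its subgroup analyses, which include the secondary safety variables, on the ITT population.

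**Follow-up.** SAP 5.1 follows every randomised patient for 90 days, "even when no neurothrombectomy is performed". Protocol 3.3 likewise follows randomised patients who are excluded on angiography.

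**The concern.** Death needs no adjudicated attribution and is recorded for every randomised patient, so it is the endpoint on which the randomised comparison is easiest to keep. As written, the plan does not keep it. Overall mortality would be grouped by what happened after randomisation, while subgroup mortality under SAP 9.4 would be grouped by randomised arm. The two sets of tables need not reconcile.

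The open cases are foreseeable. Both documents expect some randomised patients to have no thrombectomy. Non-deployment of the 3D is also plausible. The Protocol Introduction says the 3D is compatible with reperfusion catheters of 0.041 inch distal inner diameter or larger. Table 5 pairs it with the 032/3MAX catheters, which Table 3 lists at 0.032 and 0.035 inch. Those passages disagree and must be reconciled.

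Protocol 3.4 treats use of 054 or 041 separators in the 3D arm as a deviation, whereas 3.6.10 permits additional separators without that exception. Neither document says which group a patient belongs to after mixed use, or after no use, of the assigned device. SAP 3.4 leaves the investigator and the sponsor's clinical team unblinded, so the rule should be fixed in advance.

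**Working it through.** The documents give no expected mortality rate, number of deaths or power for mortality, so there is no planned mortality figure to reproduce. The sample size (103 per group, 115 after attrition) concerns the TICI endpoint and is unaffected.

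**Step 1. The rules side by side**

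| Source | Day 0 | Patients and grouping |
|---|---|---|
| Protocol 9.4, 9.4.2 | Randomisation | Only those who received the assigned treatment |
| SAP 5.1, 10.2, 10.5 | Procedure | By treatment received; membership not stated |
| SAP 9.4 (subgroups) | Not stated | ITT, by randomised arm |

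**Step 2. Three kinds of patient**

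- *No thrombectomy.* Outside the Protocol 9.4 denominator; no defined group under SAP 5.1; in the assigned arm under SAP 9.4.
- *Assigned to 3D, 3D never deployed, standard separators only.* Removed under Protocol 9.4; could be counted as control under SAP 5.1; in the 3D arm under SAP 9.4.
- *3D deployed without success, other components used afterwards.* In the 3D group on a plain reading of all three.

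**Step 3. Effect of Day 0 alone.** Protocol 3.3 randomises once the reperfusion catheter is in the target vessel, so the two dates normally coincide. Suppose the origin shifts by one day for all 230 patients, with deaths spread evenly over 90 days (assumed). The deaths affected are 230 × mortality / 90: 0.51 at 20%, 0.64 at 25% and 0.77 at 30% mortality. This is less than one death throughout.

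**Step 4. Effect of grouping.** Assumptions, none from the documents: 115 per arm; a share s of 3D patients never receive the 3D and get standard separators; their mortality is h; the rest of the arm has b = 25%; both randomised arms have the same true mortality m; no control patient receives the 3D.

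- By randomised arm, both groups: m = (1 − s)b + sh, a difference of 0.
- Counted as control: 3D = b; control = (m + sh)/(1 + s).
- Removed (Protocol 9.4): 3D = b; control = m.

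| s | h | m (both arms) | Control if moved | 3D − control, moved | 3D − control, removed |
|---|---|---|---|---|---|
| 5% | 40% | 25.75% | 0.2775/1.05 = 26.4% | −1.4 points | −0.75 points |
| 10% | 50% | 27.5% | 0.325/1.10 = 29.5% | −4.5 points | −2.5 points |
| 15% | 50% | 28.75% | 0.3625/1.15 = 31.5% | −6.5 points | −3.75 points |

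If h equals b, the distortion is zero for any s. The bias arises only if non-deployment goes with a different prognosis.

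**Step 5. Cross-check in whole deaths.** Take 29 deaths of 115 in each arm (about 25%). If five 3D-assigned deaths are counted as control: 24/110 − 34/120 = 21.8% − 28.3% = −6.5 points. If the five are removed: 24/110 − 29/115 = −3.4 points. Over assumed mortality of 20-30% the ranges are −6.1 to −7.0 and −3.2 to −3.6 points. Only patients who die are reassigned here, so this is a severe case.

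**The case against.** The strongest reply has four parts.

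1. Analysis by treatment received is a recognised convention for device safety. SAP 2 rests study success on TICI alone, so mortality decides nothing formally. That is true. It limits the severity, but it does not settle which of three populations applies.

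2. A reader might infer that the SAP departs from a protocol that kept untreated patients, and so makes their deaths disappear. The documents do not support this. Protocol 9.4 already leaves those patients out, so restoring the randomisation date would not bring them back. Nor does the SAP exclude them expressly: SAP 10.5 excludes no one, and SAP 5.1 follows them post-procedure, which suggests that they have a procedure date, since catheter placement precedes randomisation. What is missing is their treatment group.

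3. A reader might also infer that deaths after an unsuccessful 3D attempt move to control. On a plain reading they do not: a patient in whom the 3D was used has received it, and Protocol 3.4 has the 3D used first with other components following. Only a patient in whom it was never deployed is at issue.

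4. The switching and mortality inputs are assumed, and only one direction is modelled. Protocol 3.4 also foresees 3D use in control patients, which would shift patients the other way. This stands: neither the net size nor the net direction can be known from the documents.

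The Day 0 mismatch is also partly loose drafting. The protocol itself measures follow-up from randomisation (Synopsis, 3.3) and from the procedure (2.1, 3.10).

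**Conclusion.** The concern holds as a conflict and an omission. The documents give two time origins and three populations for one endpoint, and no overall mortality comparison by randomised arm is planned, although the follow-up needed for it is collected. Patients without thrombectomy have no defined group. Patients assigned to 3D who never receive it may be counted as control or removed, depending on the document followed.

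The grouping rule is what matters; the date alone affects less than one death. On the assumed inputs in Step 4, counting non-deployed 3D patients as control produces a spurious 3D advantage of about 1.4 to 6.5 points when the true difference is zero. These figures illustrate sensitivity and do not predict what the trial will show. The change should be made, but study success does not depend on it.

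**What to change.** In SAP 10.2 and 10.5, state: *All-cause mortality is analysed in all randomised patients by randomised arm, with the date of randomisation as Day 0; mortality by treatment received is supportive.*

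Three accompanying changes are needed:

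- Amend Protocol 9.4 to exempt mortality from its safety denominator. Without this, the new SAP wording would itself conflict with the protocol.
- Cite Protocol 9.4.2 for the Day 0 date only, since it does not support the all-randomised population.
- In SAP 5.1, define treatment received for the supportive analysis, covering patients with no thrombectomy and patients in whom more than one type of separator was used.

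This also brings overall mortality into line with the ITT subgroup analyses in SAP 9.4. The cost is one extra analysis and a matching protocol wording change. No new data are needed, because all randomised patients are already followed for 90 days. The wording should be settled before the SAP is signed off ahead of database lock.
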